### 9.2.2 Inclusion Criteria

Subjects must meet *all* of the following criteria:

- 1) Age 2 through 49 years (prior to 50th birthday) at the time of vaccination (or index date for unvaccinated controls)
- 2) Membership in the KP Health Care Plan for at least 12 months prior to vaccination/index date
- 3) Continuous enrollment in the KP Health Care Plan through 6 months following vaccination/index date.

There are no exclusion criteria. Subjects with any high-risk underlying medical condition as defined by ICD-9-CM codes or successor ([Annex 3](#)) will be analyzed separately.

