**Table 9.3-1 Summary of Planned Analyses**

Event of Interest	Period at Risk After Vaccination	Reference Period
Hypersensitivity MAEs a Seizures/convulsions MAEs a	0-3 days c	7-9 days d
Lower respiratory MAEs Wheezing MAEs Guillain-Barré syndrome MAEs a Bell's palsy MAEs a Encephalitis MAEs a Neuritis MAEs a Vasculitis MAEs a Any hospitalization Respiratory hospitalization b	1-42 days c (1-14 days and 15-42 days)	43-84 days
Narcolepsy/cataplexy MAEs a	1-180 days c	NA

MAE = medically attended event; NA = not applicable

a Narratives of each case will be included in the final clinical study report.

b A respiratory hospitalization will be defined by the ICD-9-CM codes sets for lower respiratory MAEs and wheezing MAEs.

c It is not possible to detect from clinical databases whether an event occurring on the day of vaccination began prior to or after administration of vaccine, although events of hypersensitivity or seizures/convulsions may occur just subsequent to vaccination but are unlikely to be recorded on the same day prior to vaccination. As a result, the period at risk after vaccination for events of hypersensitivity and seizures/convulsions begins on the day of vaccination (Day 0), and the period at risk after vaccination for all other events of interest begins 1 day after vaccination (Day 1).

d The reference period for the period at risk for 0 to 3 days was defined from 7 to 9 days to take into account cyclical variations that may occur during the same days of the week.

An MAE is defined as a coded medical diagnosis made by a health care provider and associated with a medical encounter (ie, visit to a medical clinic or emergency department, or a hospital admission). One or more MAEs could be assigned for a single encounter.

For MAEs of Guillain-Barre syndrome, Bell's palsy, encephalitis, neuritis, vasculitis, and narcolepsy/cataplexy, events will only be counted if the subject does not have a prior record of the event in the 12 months prior to vaccination (or index date for unvaccinated controls).

In addition, listings of any hospitalization within 180 days, any deaths throughout the entire study period, and exposed pregnancies throughout the entire study period will be provided.

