A hospitalization is any medical event that results in inpatient hospitalization of any duration. In general, hospitalization signifies that the subject has been detained (usually involving at least an overnight stay) at the hospital or emergency ward for observation and/or treatment that would not have been appropriate in an outpatient setting. Hospitalization for elective surgery related to a pre-existing condition that did not increase in severity or frequency following initiation of the study need not be considered a hospitalization. If anything untoward is reported during an elective procedure, that occurrence will be captured as an MAE or hospitalization according to the usual criteria.

For analyses of any hospitalization and respiratory hospitalizations (see [Table 9.3-1](#)), only the primary discharge diagnosis will be analyzed.

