### **11.1.3 Reporting of Pregnancies**

Pregnancies will be identified using pregnancy test results and additional information about first prenatal visit, births, stillbirths or spontaneous abortion diagnoses. Available information on outcomes for the mother and child (including any premature terminations) after Q/LAIV administration to known pregnant female subjects will be described in a separate listing at the conclusion of the study.

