The most common solicited adverse reactions (≥ 10% in vaccine recipients and at least 5% greater than in placebo recipients) reported after FluMist were runny nose or nasal congestion (ages 2 years through 49 years), fever over 100°F (children ages 2 years through 6 years), and sore throat (adults ages 18 years through 49 years). Among children and adolescents 2 through 17 years of age who received FluMist Quadrivalent, 32% reported runny nose or nasal congestion (32%) and 7% reported fever over 100°F. Among adults 18 through 49 years of age who received FluMist Quadrivalent, 44% reported runny nose or nasal congestion and 19% reported sore throat. (6.1)  
**To report SUSPECTED ADVERSE REACTIONS, contact MedImmune at [name] or VAERS at [name] or <http://vaers.hhs.gov>.**

----- **DRUG INTERACTIONS** -----  
• Antiviral drugs that are active against influenza A and/or B may reduce the effectiveness of FluMist Quadrivalent if administered within 48 hours before, or within 2 weeks after, receipt of the vaccine. (7.2)

----- **USE IN SPECIFIC POPULATIONS** -----  
• Safety and effectiveness of FluMist Quadrivalent have not been established in pregnant women, nursing mothers, geriatric adults, or children less than 2 years of age. (8.1, 8.3, 8.4, 8.5)  
• In clinical trials, in children 6 through 23 months of age, FluMist was associated with an increased risk of hospitalization and wheezing. (8.4)

See 17 for PATIENT COUNSELING INFORMATION and FDA-approved patient labeling. Revised: 2/2012

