**8 USE IN SPECIFIC POPULATIONS**

**8.1 Pregnancy**

**Pregnancy Category B**

A developmental and reproductive toxicity study has been performed in female rats administered FluMist Quadrivalent either three times (during the period of organogenesis) or six times (prior to gestation and during the period of organogenesis), 200 microliter/rat/occasion (approximately 150 human dose equivalents), by intranasal instillation and has revealed no evidence of impaired fertility or harm to the fetus due to FluMist Quadrivalent. There are, however, no adequate and well controlled studies in pregnant women. Because animal studies are not always predictive of human response FluMist Quadrivalent should be administered during pregnancy only if clearly needed.

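### In ages 18-49, 'any hospitalization' counts childbirth admissions while pregnancy is left unhandled, so the HR versus matched controls is biased downward wherever pregnancy is commoner among controls

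*Protocol*

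**What the plan says.** - **Endpoint (Protocol 9.3, text after Table 9.3-1).** "A hospitalization is any medical event that results in inpatient hospitalization of any duration". The one exemption begins "Hospitalization for elective surgery related to a pre-existing condition that did not increase in severity or frequency". For the hospitalization analyses, "only the primary discharge diagnosis will be analyzed". Respiratory hospitalization is limited by code sets; any hospitalization is not.
- **Window (Table 9.3-1).** Days 1-42, also split into "1-14 days and 15-42 days".
- **Eligibility (9.2.2).** "There are no exclusion criteria".
- **Label (Annex 4).** Section 8.1: "FluMist Quadrivalent should be administered during pregnancy only if clearly needed". Highlights: "Safety and effectiveness of FluMist Quadrivalent have not been established in pregnant women".
- **Matching and model (9.1, 9.7.4.2).** Controls are frequency matched on age and medical center, with vaccination month added for IIV recipients. The Cox model adjusts for age, gender, a two-level utilization variable and calendar time. Pregnancy appears in neither. It is also absent from the Annex 3 codes, so the analysis without high-risk subjects (9.9) does not remove it.
- **Pregnancy data (11.1.3).** "Pregnancies will be identified using pregnancy test results and additional information about first prenatal visit, births, stillbirths or spontaneous abortion diagnoses". The stated use is a listing of outcomes after Q/LAIV was given to women known to be pregnant.
- **Decision rule (9.7.3).** A decreased risk is declared when the upper 95% bound of the HR is below 1.00. Further assessment is foreseen for observed increases.

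**The concern.** Delivery is a common reason for admission in women of childbearing age and is not a vaccine safety outcome. Any woman who delivers in days 1-42 was already pregnant on day 0, so pregnancy status at baseline directly determines events in the risk window. The label discourages Q/LAIV in pregnancy, and nothing in the protocol similarly keeps pregnant women out of the control groups. If they are under-represented among Q/LAIV recipients, controls accrue delivery admissions that Q/LAIV recipients do not.

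Two consequences follow for the adult between-group comparison. A spurious decreased risk could be declared under the rule in 9.7.3. A real increase in other admissions could be offset, and because follow-up is tied to observed increases, this comparison would not trigger it.

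**Working it through.** **The plan's own figures.** The protocol gives no figure for this issue. Its sample-size statement in 9.5 reproduces and is not in dispute. With two proportions, equal groups and two-sided 0.05, 10,000 per group at 1.0% versus 1.5% gives power 0.889, and 20,000 per group at 0.5% versus 0.75% gives 0.887. Both match the stated 90% approximately.

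**Inputs (ages 18-49).** None of these is in the documents; all are assumptions.
- o = non-obstetric admissions per 1,000 person-years: 20-60
- d = deliveries per 1,000 woman-years in controls: 30-100
- f = share of women: 0.5-0.6
- r = delivery rate in Q/LAIV recipients relative to controls: 0-0.5

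**Formula.** With no vaccine effect, expected HR = (o + f·d·r) / (o + f·d).

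Results for f = 0.5:

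| o | d | r = 0 | r = 0.1 | r = 0.25 | r = 0.5 |
|---|---|---|---|---|---|
| 20 | 50 | 0.44 | 0.50 | 0.58 | 0.72 |
| 40 | 50 | 0.62 | 0.65 | 0.71 | 0.81 |
| 60 | 30 | 0.80 | 0.82 | 0.85 | 0.90 |

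Ends of the full grid: o = 20, d = 100, f = 0.6, r = 0 gives 20/80 = 0.25. o = 60, d = 30, f = 0.5, r = 0.5 gives 67.5/75 = 0.90.

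**Effect on the decision rule.** Take 20,000 adults per group, inside the 10,000 to 30,000 that 9.5 expects for Q/LAIV, with equal-sized control groups assumed. Person-years = 20,000 × 42/365.25 ≈ 2,300.
- Central case (o = 40, d = 50, f = 0.5, r = 0.1): rates 42.5 and 65 per 1,000, so about 98 versus 149 events. HR = 42.5/65 = 0.65, 95% CI 0.51 to 0.84. The chance of declaring a decreased risk is about 90%. A true RR of 1.5 for non-obstetric admissions reads (60 + 2.5)/65 = 0.96.
- Mildest case (o = 60, d = 30, f = 0.5, r = 0.5): about 155 versus 172 events, HR 0.90, 95% CI 0.72 to 1.12. The chance of a declared decrease is about 16%. A true RR of 1.5 reads (90 + 7.5)/75 = 1.30.

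**Do gender and utilization remove it?** Pregnancy varies within women and within the high-utilization class. Central case, four strata of sex by utilization, all deliveries in the high class, that class 30% or 50% of subjects and equally common in both groups, with a non-obstetric rate 2 or 3 times that of the low class: the HR in high-utilization women is 0.34 to 0.44 and the combined HR stays at 0.65. If pregnancy itself makes the high class commoner among controls, adjustment would remove part of the bias.

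**All ages pooled.** Let s be the adult share: 10,000/80,000 = 0.125 to 30,000/80,000 = 0.375. Let c be the admission rate below age 18, assumed 8-15 per 1,000 person-years with no deliveries. HR = [(1−s)c + s(o + f·d·r)] / [(1−s)c + s(o + f·d)].
- s = 0.375, c = 8, central adult case: (5 + 15.94)/(5 + 24.38) = 0.71.
- s = 0.125, c = 15, adult case o = 60, d = 30, f = 0.5, r = 0.25: (13.13 + 7.97)/(13.13 + 9.38) = 0.94.

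This range covers those two adult cases, not the full adult grid.

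**The case against.** The strongest reply is that the size rests wholly on outside rates, and that the protocol has other safeguards.

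- **Size and degree of imbalance.** A reader might infer that pregnant women will be nearly absent from the Q/LAIV group and that both HRs will fall well below 1. The documents do not support that. Pregnancy is not among the contraindications in Annex 4, the label wording is a caution, and the protocol expects some exposed pregnancies because it plans a listing. Pregnancy prevalence is given for neither control group and may differ between IIV recipients and the unvaccinated. This objection stands: direction is conditional for each comparison, and size is a range.
- **Pooled analysis.** A reader might infer that deliveries dominate the 2-49 result. Adults are only 12.5-37.5% of the expected cohort, and the pooled bias is weaker. This stands.
- **Parallel analyses.** Any hospitalization is also compared within the Q/LAIV cohort, days 1-42 versus 43-84, with no between-group imbalance. Respiratory hospitalization is defined by respiratory codes. All hospitalizations within 180 days are listed. So it would be wrong to infer that the whole study could miss an increase; the masking applies to the between-group comparison. This stands.
- **Acknowledged limitation.** Sections 9.1 and 9.9 admit residual differences and indication bias, and the study is hypothesis generating. A generic caveat does not help a reader interpret an HR shifted by a known, removable event type.
- **The SAP.** A delivery filter could sit in a SAP that is not shown. But the protocol itself fixes the endpoint, its single exemption, eligibility, matching and covariates. A SAP that followed them faithfully would reproduce the bias.

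**Conclusion.** The concern holds for the comparison of any hospitalization with matched controls in ages 18-49. The mechanism follows from the text. The HR is biased downward against a given control group if pregnancy is more common there than among Q/LAIV recipients, which the label makes plausible but the documents do not quantify.

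Under the assumed ranges the distortion runs from modest to severe, and at the mild end a false declaration of decreased risk is unlikely. The FDA commitment population, ages 2-8, is untouched, as are the within-cohort and respiratory hospitalization analyses. This should be corrected, but it does not undermine the study's main purpose.

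**What to change.** In 9.3, add a second exemption beside the one for elective surgery: admissions whose primary discharge diagnosis is an obstetric delivery do not count toward any hospitalization, in all three groups. The field is already the one analyzed, so this is a code filter. It removes the delivery term from both numerator and denominator, and the expected null HR returns to o/o = 1.00 as far as this source of bias goes.

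Optionally, add an adult matched analysis that leaves out women with a recorded pregnancy on the vaccination or index date from all three groups. This would also deal with pregnancy-related admissions other than delivery. It costs more, because 11.1.3 clearly plans pregnancy outcomes only for Q/LAIV recipients; identification would have to be extended to controls from the same databases.

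Keep the exposed-pregnancy listing. The small downside is that delivery admissions would then be described only there and in the 180-day hospitalization listing.

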#### **9.4 Data Sources**

Study data are derived directly from NCKP clinical and institutional databases, which are not research databases. Rather they make up the electronic medical record documenting vaccine administration, medical utilization, participant demographics, and HMO membership for all NCKP members.

#### **9.5 Study Size**

Since there are no identified safety concerns with Q/LAIV, this post-marketing safety assessment is hypothesis generating and will include multiple statistical comparisons.

Enrollment of at least 10,000 children 2 through 8 years of age is planned. A sample size of 10,000 children will provide approximately 90% power to observe a statistically significant increase in relative risk (RR) of 1.5 for an event that occurs in 1 in 100 subjects in the comparison group. The study will also be able to rule out with 95% probability the occurrence of an event at a rate of 0.03% (1 in 3,333 subjects) assuming that incidence of the event follows a Poisson distribution. Enrollment is expected to be completed in the 2013-2014 influenza season but the study will be continued for additional seasons, if needed, until enrollment of 10,000 Q/LAIV recipients 2 through 8 years of age is completed to fulfill the postmarketing commitment to the FDA.

However, because the study is expanded to adolescents and adults up to 49 years of age, it is expected that a total of approximately 80,000 individuals will be enrolled (including approximately 10,000 to 30,000 individuals in each of the following 4 age groups: 2 to 4 years, 5 to 8 years, 9 to 17 years, and 18 to 49 years of age) during the 2013-2014 influenza season. Enrollment of 20,000 children per age group will provide approximately 90% power to observe a statistically significant increase in relative risk (RR) of 1.5 for an event that occurs in 1 in 200 subjects in the comparison group. A sample size of 20,000 will also be able to rule out with 95% probability the occurrence of an event with an incidence rate of 0.015% (1 in 6,666 subjects).

## 9.6 Data Management

NCKP clinical databases are maintained by Kaiser Permanente Information Technology (IT). This information is tracked with an automated audit trail (eg, adds, deletes, updates to study records). This information is stored on a secure SQL server that is administered, secured, backed up, and maintained by Division of Research IT personnel.

## 9.7 Data Analysis

### 9.7.1 Analysis Populations

The populations to be assessed are all Q/LAIV recipients and the nonrandomized control groups (unvaccinated subjects, and IIV recipients) as described in Section 9.1.

Analyses will also be performed by age group (2 to 4 years, 5 to 8 years, 9 to 17 years, 18 to 49 years) and setting (clinic, hospital, emergency department).

Q/LAIV recipients with medical conditions that are a warning/precaution against the use of Q/LAIV (see Package Insert; [Annex 4](#)) will be analyzed separately. Subjects will be identified as having these conditions by using the International Classification of Diseases Clinical Modification (ICD-9-CM or successor) diagnosis codes as outlined by [Daley et al, 2004](#) (see [Annex 3](#)).

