Q/LAIV was approved by the US FDA on 29Feb2012 for individuals 2 to 49 years of age, and it will be marketed in the USA beginning in the 2013-2014 influenza season. The approval was predicated on conducting an observational postmarketing safety surveillance study in children 2 through 8 years of age. The current study implements this postmarketing commitment between MedImmune and the US FDA, and provides an expanded safety profile of Q/LAIV in the indicated populations by including vaccine recipients between 9 and 49 years of age

The design of this observational postmarketing safety surveillance study is consistent with current vaccine safety monitoring practices ([Andrews, 2002](#); [Yih et al, 2011](#)) and the conduct of previous post-authorization safety studies of FluMist in subjects 5 to 49 years of age (Study FM025 [[Baxter et al, 19Apr2012](#); [Baxter et al, 26Apr2012](#)] and in subjects 24 to 59 months of age (Study MI-MA162 [[Toback et al, 2013](#)]) required by the US FDA. In those studies, the incidence of medically attended events (MAEs) following FluMist receipt was compared between 2 time intervals following vaccination as well as versus matched unvaccinated controls and matched inactivated influenza vaccine (IIV) recipient controls. The results of these studies demonstrated no significant adverse outcomes following receipt of FluMist among eligible individuals.

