## 9.7.3 Planned Analyses

Tabular summaries will be presented by treatment group. Categorical data will be summarized by the number and percentage of subjects in each category. Continuous variables will be summarized by descriptive statistics, including mean, standard deviation, median, minimum, and maximum. The age, gender, medical center, and prior year health care utilization level of the Q/LAIV and control groups will be summarized for descriptive purposes. Race information is not available in the Kaiser HMO databases.

Rates of events will be presented per 1,000 person-years. All statistical tests will be 2-sided and performed at the significance level of 0.05. Due to the exploratory nature of the study and the lack of formal hypothesis testing, multiple CIs will be constructed in the primary analysis without multiplicity adjustment. Due to the large number of unadjusted CIs to be evaluated, it is expected by chance alone that a number of CIs will not include one and suggest higher or lower event rates in the Q/LAIV group. Therefore, further statistical and medical assessments may be performed for events with observed increases that are statistically significant and/or medically important.

Incidence rates of adverse events of interest during periods at risk after Q/LAIV vaccination will be compared to incidence rates during reference periods later in the follow-up as presented in [Table 9.3-1](#) (within-cohort analysis) and to incidence rates in controls (matched unvaccinated subjects and matched IIV recipients).

Incidence rates will be reported as subjects with an event per 1,000 person-years. If a subject has more than one event in the analysis window, the subject will be counted only once for the analysis. Relative risks (RR) and corresponding 95% CIs will be constructed for each event for safety comparisons with control groups. Crude RR and adjusted hazard ratio (HR) and corresponding 95% CIs for each event will be derived:

- Crude RR and exact 95% CI will be calculated without adjustment of any covariate.
- Adjusted HR and corresponding 95% CI will be obtained using Cox proportional hazards model with calendar time data input adjusting for seasonal changes in

background rates and other confounders. This multivariable analysis is detailed in Section 9.7.4.

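### Section 9.7.1 lists no analysis of children 2 through 8, the group on which the commitment, the 10,000 minimum and the 90% power are defined

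*Protocol*

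**What the plan says.** Section 7 gives the origin of the study: "The approval was predicated on conducting an observational postmarketing safety surveillance study in children 2 through 8 years of age". Section 9.5 sets the floor, "Enrollment of at least 10,000 children 2 through 8 years of age is planned", and continues the study into further seasons if necessary "until enrollment of 10,000 Q/LAIV recipients 2 through 8 years of age is completed to fulfill the postmarketing commitment to the FDA". The main power statement belongs to the same children: "A sample size of 10,000 children will provide approximately 90% power to observe a statistically significant increase in relative risk (RR) of 1.5". It assumes that 1 in 100 comparison subjects has the event.

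Section 9.7.1 defines what is analyzed. It begins with everyone: "The populations to be assessed are all Q/LAIV recipients and the nonrandomized control groups (unvaccinated subjects, and IIV recipients) as described in Section 9.1". It then adds: "Analyses will also be performed by age group (2 to 4 years, 5 to 8 years, 9 to 17 years, 18 to 49 years", together with a breakdown by care setting and a separate analysis of recipients with warning or precaution conditions. No 2 through 8 group appears there, in Section 9.7.3 or in the model descriptions of Section 9.7.4.

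Section 9.5 also expects about 80,000 recipients in total, with 10,000 to 30,000 in each of the four age groups. It gives a second power statement for 20,000 per group and a 1-in-200 event.

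**The concern.** The population that sets the minimum size, and decides whether another season is needed, is not an analysis population. A reader looking for the result that answers the commitment would find two separate results, for 2-4 and 5-8 years, and one result for 2-49 years that mixes in adolescents and adults.

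Two things are at stake. First, the estimate for ages 2 through 8, with its confidence interval, is not produced at any enrollment. Second, if enrollment is close to the floor, the 90% quoted for 10,000 children does not describe either of the two pediatric results. An increase specific to ages 2-8 could then go undetected more often than Section 9.5 suggests.

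**Working it through.** **Inputs from the protocol.** Comparison risk 1 in 100 and RR 1.5, so 0.010 against 0.015 (Section 9.5). Two-sided tests at 0.05 (Section 9.7.3). Minimum 10,000 recipients aged 2-8 (Section 9.5).

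**Assumptions.** Section 9.1 specifies frequency matching but gives no ratio of controls to recipients, so 1:1 is the base case and 1:2 and 1:3 give the range. The division of the 10,000 between 2-4 and 5-8 is not stated either. An even split is the base case and uneven splits are shown.

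**Formula.** Two-proportion normal approximation, with n1 comparators at risk p1 and n2 recipients at risk p2:

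- power = Φ[(|p2 − p1| − 1.96·se0)/se1]
- se0 = √[p̄(1 − p̄)(1/n1 + 1/n2)], where p̄ is the pooled risk
- se1 = √[p1(1 − p1)/n1 + p2(1 − p2)/n2]

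**Step 1: reproduce the plan's figure.** With 10,000 per arm, 1.96·se0 = 0.00308 and se1 = 0.00157. Power = Φ[(0.00500 − 0.00308)/0.00157] = Φ(1.22) = 88.9%. A Schoenfeld calculation with 250 expected events and a hazard ratio of 1.5 gives 89.4%. The stated figure of about 90% is reproduced if the 10,000 children form one analysis with 10,000 comparators.

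**Step 2: the two listed pediatric groups at the minimum.** With 5,000 per arm, 1.96·se0 = 0.00436 and se1 = 0.00222. Power = Φ[(0.00500 − 0.00436)/0.00222] = Φ(0.29) = 61.4%.

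| Recipients in the group | 1:1 | 1:2 | 1:3 |
|---|---|---|---|
| 3,000 | 41.4% | 54.6% | 60.3% |
| 4,000 | 52.1% | 66.1% | 71.8% |
| 5,000 | 61.4% | 75.2% | 80.4% |
| 6,000 | 69.3% | 82.2% | 86.5% |
| 7,000 | 75.9% | 87.4% | 90.9% |
| 10,000 (pooled 2-8) | 88.9% | 95.8% | 97.4% |

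A 3,000/7,000 split with three controls per recipient brings the larger group to 90.9%, but the smaller then has 60.3%. In none of these splits do both groups reach the stated figure.

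**Step 3: the 2-49 analysis at the same minimum.** It contains all 10,000 children. For an RR of 1.5 common to all ages, its power is 88.9% if nobody older is enrolled and 99.4% with 20,000 recipients in total.

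Now suppose the RR of 1.5 is confined to the 10,000 children, with a 1% baseline at every age, RR 1 at 9-49 and 1:1 controls. The overall RR in N recipients is 1 + 0.5 × 10,000/N:

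- N = 20,000: RR 1.25, so 0.0100 against 0.0125, and power is about 66%.
- N = 50,000: RR 1.10, so 0.0100 against 0.0110, and power is about 34%.

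**Step 4: expected enrollment.** With 10,000 to 30,000 in each of 2-4 and 5-8, each group alone has 88.9% to above 99.9% for the 1-in-100 event at 1:1.

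**The case against.** The strongest reply is that the shortfall is unlikely to occur. The 10,000 is a floor and not a closing point: the plan takes all eligible recipients of the 2013-2014 season and adds seasons only if fewer than 10,000 children are found. At the expected enrollment, each pediatric group alone reaches the stated power (Step 4). The study is also declared hypothesis generating, and a pooled 2-8 table could be added in a statistical analysis plan that was not available for this review. A split at age 5 has some basis in the annexed label, whose wheezing warning singles out children under 5. All of this stands and limits the severity. It does not supply the missing group: Section 9.7.1 itself fixes the age groups, and enrollment above the floor does not create a 2-8 estimate.

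Three stronger readings are tempting, and the documents do not support them:

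- A reader might infer that no planned analysis has the stated power at the minimum. The 2-49 analysis has at least 88.9% for an effect common to all ages, and the two older groups could also reach 10,000.
- A reader might fault the sentence on 20,000 per group because 10,000 to 30,000 are expected. That sentence is conditional and correct (88.7% by the same formula). It is also consistent with 80,000/4 = 20,000.
- A reader might infer that the agency required a pooled 2-8 estimate, or that older subjects will dominate the overall result. The protocol says only that a study in this age range was required. On its own ranges, ages 2-8 could be 20,000 to 60,000 of about 80,000.

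**Conclusion.** The point holds as an omission in Section 9.7.1: the age range that carries the commitment, the minimum and the 90% power is not listed as an analysis group. This is so at any enrollment and rests on no assumption.

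The loss of power is conditional. It arises only if enrollment of children 2-8 is near 10,000, and the 61%, 75% and 80% per group depend on an assumed even split and on the control ratio. The fall to about 66% to 34% in the 2-49 analysis depends on an effect confined to ages 2-8, equal 1% baseline risks, 20,000 to 50,000 recipients and 1:1 controls. The power figures in Section 9.5 are themselves sound. The correction is worth making because it is simple, but the study's size and design do not need to change.

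**What to change.** In Section 9.7.1, add 2 through 8 years as a prespecified analysis group, for every event of interest and for all three comparisons (within-cohort, unvaccinated controls, IIV controls). Keep the 2-4 and 5-8 groups. State that the 2 through 8 analysis is the one that addresses the postmarketing commitment. In Section 9.5, say that the power of about 90% for 10,000 children refers to that group.

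This restores 88.9% at the minimum (1:1) without more subjects or more data. The cost is one more set of tables and a further set of unadjusted confidence intervals, in a study that already expects some of them to exclude one by chance.
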